### 6.2 Secondary objectives

1. To estimate the incidence of angioedema, hypotension, hyperkalemia, hepatotoxicity, and renal impairment in adult HF patients newly starting treatment with ACEIs (patients without prior exposure of ACEIs/ARBs)
2. To estimate the incidence of angioedema, hypotension, hyperkalemia, hepatotoxicity, and renal impairment in adult HF patients with ACEI exposure (regardless of prior use of ACEIs or ARBs)

### 6.3 Exploratory objectives

1. To estimate the relative risk of angioedema in adult HF patients newly starting treatment with sacubitril/valsartan (without prior ACEI/ARB exposure) as compared to adult HF patients newly starting treatment with ACEIs (without prior ACEI/ARB exposure)

2. To estimate the relative risk of angioedema in adult HF patients newly starting treatment with sacubitril/valsartan (regardless of prior ACEI/ARB exposure) versus adult HF patients newly starting treatment with ACEIs (without prior ACEI/ARB exposure)
3. To estimate the relative risk of angioedema in adult HF patients newly starting treatment with sacubitril/valsartan (regardless of prior ACEI/ARB exposure) versus adult HF patients with ACEI exposure (regardless of prior ACEI/ARB exposure)

All comparative analyses in this study are considered exploratory due to potential biases that exist related to selecting patients on ACEI treatment who are either treatment-naïve to ACEIs and ARBs or are prevalent ACEI users as our comparator group (see also [Section 7.1.1](#) and [Section 7.9](#)).

## 7 Research methods

### 7.1 Study design

This is a non-interventional cohort study using European healthcare database information in a population of adult patients with prevalent or incident HF, newly starting treatment with sacubitril/valsartan (with or without prior exposure to ACEIs or ARBs), or ACEIs (as new users, and separately as prevalent users); see [Section 7.3.1](#) for more details on exposure cohort classifications.

#### 7.1.1 Rationale for study design

To obtain a robust estimate of the incidence of angioedema – the primary safety event of interest – as well as of the other safety events (i.e. hypotension, hyperkalemia, hepatotoxicity, and renal impairment) in patients newly starting sacubitril/valsartan (incident users), an initial cohort of all sacubitril/valsartan initiators will be identified (regardless of prior exposure to ACEIs or ARBs) with patient accrual beginning at the specific launch date of sacubitril/valsartan (see [Table 7-1](#)) in those EU countries from which healthcare database information will be used for this study (see [Section 7.4](#) ‘Data sources’). In addition, an initial contemporaneous comparator cohort of ACEIs initiators will be identified. Data collection will end when the necessary sample size of 24,000 PYs is reached (see [Section 7.5](#) ‘Study size/power calculation’), but on 31 December 2021 at the latest (even when the target sample size is not reached).

A new user design ([Ray 2003](#), [Food and Drug Administration 2013](#), [Yoshida et al 2015](#)) is proposed to minimize the risk of a prevalent user bias and depletion of susceptibles. This is of particular importance for ACEIs users. Sacubitril/valsartan was newly introduced to the market and the cohort of users therefore automatically consists of new users. As indicated in the sacubitril/valsartan ‘Summary of Product Characteristics’ (SmPC), it is contraindicated for patients with a known history of angioedema related to previous ACEI or ARB therapy, or with hereditary or idiopathic angioedema. The combination of sacubitril/valsartan with an ACEI is contraindicated due to the increased risk of angioedema. Sacubitril/valsartan must not be initiated within 36 hours after taking the last dose of ACEI therapy.

Since the majority of sacubitril/valsartan users are expected to have been treated with an ACEI or ARB before starting sacubitril/valsartan, these patients will likely have a lower baseline risk of angioedema as susceptible patients have been depleted. ACEI initiators who are treatment

naïve to ACEIs and ARBs however, will likely have a higher baseline risk of angioedema since this population includes all patients who are susceptible to an angioedema event.

As the risk of ACEI-associated angioedema is highest very shortly after treatment initiation and decreases over time ([Kostis et al 2005](#), [Miller et al 2008](#), [Toh et al 2012](#)), a cohort of prevalent ACEI users would be biased towards a lower angioedema risk compared to ACEI naïve patients. The majority of patients experiencing angioedema while treated with ACEIs can be expected to discontinue ACEI treatment and would therefore unlikely be part of a prevalent ACEI user cohort. Thus, comparing sacubitril/valsartan initiators regardless of their prior exposure to ACEIs/ARBs, to ACEI initiators who are treatment naïve to ACEIs and ARBs is likely to bias the comparative (explorative) analysis in favor of sacubitril/valsartan. Therefore, it is considered that the optimal comparison is between sacubitril/valsartan initiators who are treatment naïve to ACEIs/ARBs and ACEI initiators without prior ACEIs/ARB use. To provide an estimate of what may happen if prevalent users are included, we will explore all these analyses (see [Section 6.3](#) Exploratory objectives).

Accruing the required sample size for the comparison of patients initiating sacubitril/valsartan treatment without prior ACEI/ARB use with those newly initiating treatment with ACEIs/ARBs within the proposed timelines will be very unlikely. It should be expected that many HF patients (both prevalent and incident) will have been previously exposed to an ACEI used as treatment for hypertension or other comorbid diseases prevalent in HF patients (e.g., acute myocardial infarction, diabetic nephropathy). A US study in patients with incident HF diagnosed between 2005 and 2008 from four sites participating in the Cardiovascular Research Network (CVRN) found an exposure prevalence to ACEIs or ARBs in patients with incident HFrEF (n=3,941, mean age 69 years) of 43% ([Goldberg et al 2013](#)). In the European ‘ESC-HF Long-Term Registry’ a prospective cohort study with primary data collection, including over 7,400 patients with prevalent chronic HF (median age 66 years) were enrolled over two years. In the subgroup of patients with HFrEF (n=4,792), 92.2% were treated with ACEIs or ARBs at baseline ([Maggioni et al 2013](#)). Thus, indicating that the absolute number of ACEI initiators who are treatment naïve to ACEIs and ARBs will be limited. If necessary, it was initially planned to supplement the contemporaneous comparator cohort with a historical cohort of ACEI initiators who are treatment naïve to ACEIs using data prior to Entresto® market approval if needed. However, the most recent interim report for the LCZ696B2014 study identified a total of 116,041 ACEI initiators being treatment naïve to ACEIs/ARBs [REDACTED] when both ARS and GePaRD were included. Based on these results, inclusion of a historical cohort of ACEI initiators treatment naïve to ACEIs/ARBs does not seem necessary.

In addition, to explore the impact of depletion of susceptibles we will assess the rate of events in users of ACEIs with prior use of ACEIs/ARBs.

### 7.1.2 Feasibility assessments

The following feasibility assessments were conducted to inform the design of the study and to provide information on its limitations:

1. To describe the numbers and characteristics of ACEIs users over time (annually; 2011 to most recent year available for each data partner), stratifying users into those who are treatment-naïve and non-naïve to ACEIs and ARBs, and estimate standardized differences in characteristics over time

2. To investigate the potential gap in available sacubitril/valsartan prescriptions (or pharmacy fills) due to specialist prescribing in or outside the hospital, and its potential impact on the objectives of the study LCZ696B2014, especially at treatment initiation in the different databases
3. To assess event rates in the general adult population of the safety outcomes of angioedema, hypotension, hyperkalemia, hepatotoxicity, and renal impairment based on different algorithms for the LCZ696B2014 study, and to harmonize the codes used to detect these outcomes across the various databases
4. To assess how each database can best assess the severity of HF
5. To assess the indication of sacubitril/valsartan users without recorded HF diagnosis

A high-level summary of the feasibility results for each objective relevant for study LCZ696B2014 is provided below (for more details, see [REDACTED]):

[figure not shown]
*Ad objective 1:* No major differences were observed in the characteristics of ACEI users before and after launch of sacubitril/valsartan, indicating that ACEI users from the period before launch could be included as a historical ACEI cohort to complement contemporaneous ACEI initiators. However, the fourth interim report of the LCZ696B2014 study identified >89,000 HF patients in “ACEI cohort 3” (ACEIs users regardless of prior ACEI/ARB use [i.e., mix of prevalent and incident ACEI users]) and almost 567,000 ACEI users when using data from ARS and GePaRD databases. In cohort 4 (ACEIs users without prior use of ACEIs/ARBs [i.e., treatment-naïve ACEI users]) >21,500 HF patients were identified and >116,000 HF patients when data from ARS and GePaRD was included. As this number will further increase until the final LCZ696B2014 analyses, an addition of historical ACEI users is not required.

*Ad objective 2:* The potential gap in sacubitril/valsartan prescriptions (or pharmacy fills) due to specialist prescribing in or outside the hospital was assessed by the number of patients with a hospitalization or referral to a specialist in the 3 months prior to the index date. A substantial proportion of sacubitril/valsartan users included in the feasibility study cohort were in specialist/ambulatory care (proportion ranged from 17% in Aarhus to 72% in HSD) or hospitalized within 3 months prior to the first sacubitril/valsartan prescription (proportion ranged from 18% in HSD to 42% in GePaRD). The time between referral or hospitalization for HF and first identified sacubitril/valsartan prescription (or pharmacy fill) in CPRD, HSD, GePaRD, and PHARMO was between 0 and 20 days for most sacubitril/valsartan users. In SIDIAP, this was more than 30 days for most patients. It seems plausible that for a number of these patients the first sacubitril/valsartan prescription may have been missed, either because inpatient prescribing is not present in all databases or outpatient specialist prescriptions are not captured (CPRD, HSD). The impact of misclassification of treatment start cannot be assessed with sensitivity analyses, because patients with an angioedema event during treatment that is not captured, will not have subsequent out-patient prescription records for sacubitril/valsartan that are captured, and therefore will not be included in the sacubitril/valsartan cohorts. If initiation of sacubitril/valsartan use is missed, but later exposure is captured, exposure time will be slightly underestimated and safety event rates may be slightly overestimated.

*Ad objective 3:* Crude and age-/sex-standardized event rates were calculated for the safety events of interest in the general (adult) database population and were compared across databases overall and by data provenance.

As an example, [Figure 7-1](#) displays the assessment of safety event rates for angioedema (*'narrow'* definition).

**Figure 7-1 Age- and sex-standardized safety event rates of angioedema (*'narrow'*) in a general adult population by provenance over time**

Results suggest that all databases are able to capture the safety events of interest. The extent to which each safety event is captured differs per database and depends on the setting in which the data were captured (primary or secondary care), the granularity of the corresponding coding system(s), and the organization of healthcare in each country. For GePaRD, 12 algorithms for the confirmation of recorded diagnoses were tested and evaluated. [Table 12-1](#) includes the final choice of algorithm made by GePaRD after discussion with both investigators and German physicians with knowledge of the healthcare system and recording practices. For angioedema, an algorithm of one discharge diagnosis (main or secondary) or two outpatient diagnoses from different physicians within up to three months was considered to be the most reliable algorithm for a confirmed diagnosis of angioedema.

Code harmonization for the safety events of interest resulted in exclusion of unspecific diagnoses and differentiation of *'narrow'* and *'broad'* diagnosis definitions for angioedema and hypotension, to allow exploration of specificity and sensitivity of captured results in the final analysis for study LCZ696B2014. The specificity of all safety events of interest based on the harmonize code list are further examined in a validation study.

*Ad objective 4:* Of 5,185 adult sacubitril/valsartan initiators with recorded HF diagnosis and sufficient history and follow-up identified across the seven databases, GePaRD contributed

most sacubitril/valsartan initiators (N=4,724) [REDACTED]. Whereas GePaRD, ARS, and PHARMO cannot provide any information on HF severity. HSD and SIDIAP captured information on left ventricular ejection fraction (LVEF), and Aarhus, CPRD, HSD, and SIDIAP captured information on NYHA classification. However, all information of HF severity is only available for a relatively small proportion of patients in each database (10-20%). HSD and SIDIAP also captured information on HF phenotype. For HF treatment, only the number of medications is recorded in all databases whereas the dose is not captured at the same level of detail. The number of drug classes used in the treatment of HF could be a good overall measure of HF severity and would be possible to be included as proxy for HF severity.

Any effect of the severity of HF in relation to the safety events of interest in the LCZ696B2014 study (in particular with respect to angioedema) is expected to be marginal, and likely to be mediated through comedication use rather than ejection fraction per se.

*Ad objective 5:* A patient profile review was performed to assess the putative alternative indication of sacubitril/valsartan users without recorded HF diagnosis. The review showed that alternative cardiac diagnoses such as coronary artery disease, myocardial infarction and heart arrhythmias were found in the majority of sacubitril/valsartan users without a recorded HF diagnosis. In addition, due to the reimbursement conditions for sacubitril/valsartan it is likely that HF was present although not recorded separately from the underlying cardiovascular disease. Sensitivity analyses of all sacubitril/valsartan users regardless of a recorded HF diagnosis record were conducted as part of the third and fourth interim reports of study LCZ696B2014. No differences in IRs for any safety event were observed when compared to IRs for all sacubitril/valsartan users with HF diagnosis. Thus, no sensitivity analysis is planned for the final analysis of the LCZ696B2014 study.

## 7.2 Setting

### 7.2.1 Source population

The source population for this study will be based on patient-data from seven EU electronic healthcare databases:

- the ‘Sistema d’Informació per al Desenvolupament de la Investigació en Atenció Primària’ (SIDIAP) from Catalonia, Spain (ES)
- the ‘PHARMO Database Network’ (PHARMO) from the Netherlands (NL)
- the ‘Health Search IMS Health Longitudinal Patient Database’ (HSD) from Italy (IT)
- the ‘Aarhus University Prescription Database’ (Aarhus) and Danish National Patient Registry from Denmark (DK)
- the Clinical Practice Research Datalink (CPRD) from the United Kingdom (UK)
- the German Pharmacoepidemiological Research Database (GePaRD) from Germany (DE)
- the Agenzia Regionale di Sanità della Toscana (ARS) from IT

### 7.2.2 Study population

The overall study population will consist of adult patients ( $\geq 18$  years of age) initiating either sacubitril/valsartan or using an ACEI/ARB during the study period and having a recorded

diagnosis of HF in the database prior to or within three months (90 days) after the first prescription (or pharmacy fill) of sacubitril/valsartan or ACEI in the study period.

HF patients will be identified using both recorded inpatient and/or outpatient diagnoses based on the specific coding system used by the individual database (e.g. READ in CPRD, International Classification of Diseases, 9th Revision, Clinical Modification (ICD-9 CM) in HSD and ARS, ICD-10 CM in SIDIAP, PHARMO, CPRD (HES), and Aarhus University Prescription Database and the Danish National Patient Registry, ICD-10 German Modification (GM) in GePaRD, and International Classification of Primary Care codes [ICPC] and “Werkgroep Coördinatie Informatisering en Automatisering” codes (WCIA) in PHARMO; see also [Table 7-8](#)).

### 7.2.3 Study period

The study period during which patients can enter the study population will start at the sacubitril/valsartan launch dates in the countries of interest (see launch dates in [Table 7-1](#) below) and will end on the 30th of April 2021 at the latest. The total study time frame (including the beginning of the minimal 365 days look-back period before cohort entry) will begin in December 2014 at the earliest. With a data extraction date in December 2021, the end of data availability will range from December 2019 (GePaRD) through April 2021 (ARS).

**Table 7-1 Sacubitril/valsartan launch date in the countries of interest and study duration by database**

Country (database)	Launch date	Expected end of data availability	Duration of study period
Aarhus (Denmark)	December 2015	December 2020	61 months
GePaRD (Germany)	January 2016	December 2019	48 months
ARS, HSD (Italy)	April 2016 (reimbursement March 2017)	December 2020 (HSD); April 2021 (ARS)	57 months (HSD); 61 months (ARS)
PHARMO (Netherlands)	July 2016	December 2020	54 months
SIDIAP (Spain)	October 2016	June 2021	57 months
CPRD (United Kingdom)	December 2015	December 2020	61 months

### 7.2.4 Inclusion and exclusion criteria

#### Inclusion criteria

Patients will be required to:

- Have initiated sacubitril/valsartan or using an ACEI during the study period
- Be aged  $\geq 18$  years at the time of the first prescription (or pharmacy fill) for sacubitril/valsartan or an ACEI. If the exact date of birth is not known, January 1st of the calendar year the patient turns 18 years will be the start date when only the year is known, and the first date of the month when the month and the year are known
- Have a recorded diagnosis of HF in the database prior to or within three months (90 days) after the first prescription (or pharmacy fill) of sacubitril/valsartan or ACEI in the study period

- Have  $\geq 365$  days of valid database history prior to the first prescription (or pharmacy fill) for sacubitril/valsartan or an ACEI (i.e., the patient was registered in the database for at least one year)

*Note:* In GePaRD, only confirmed diagnoses of HF will be selected by using the following algorithm based on records with a confirmed diagnosis status:

- At least one primary hospital discharge diagnosis of HF
- OR at least two outpatient HF diagnoses

In all cases, the first recorded claims date in the context of a HF diagnosis will be considered as the diagnosis date. In all other databases one diagnosis of HF from in- and/or outpatient registry data or electronic medical records will be used.

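### In GePaRD, heart failure may be confirmed by a record made long after index yet is dated to the earliest insurance record, so cohort entry depends on post-index survival and enrolment

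*Protocol*

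**What the plan says.** Section 7.2.4 of the protocol sets the HF criterion for all databases: "Have a recorded diagnosis of HF in the database prior to or within three months (90 days) after the first prescription". A note then restricts GePaRD to confirmed HF, reached by either of two routes:

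- "At least one primary hospital discharge diagnosis of HF"
- "OR at least two outpatient HF diagnoses"

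Neither route has a latest date, and the outpatient route has no limit on the gap between claims. The dating rule follows: "In all cases, the first recorded claims date in the context of a HF diagnosis will be considered as the diagnosis date". Elsewhere a single record is enough: "In all other databases one diagnosis of HF from in- and/or outpatient registry data or electronic medical records will be used".

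Follow-up starts at the first recorded prescription or fill (Section 7.2.5). It ends at the outcome, death, end of data, or stopping, switching or adding treatment (Section 7.2.6).

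For angioedema in the same database, Section 7.1.2 does bound the confirming record in time: "two outpatient diagnoses from different physicians within up to three months".

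**The concern.** Eligibility should be decided from information available by the eligibility cut-off. Here the window of 90 days after index is tested against the date of the earliest HF record, while the record that makes it count may lie well beyond it. Patients whose record ends early are removed, and those who stay long enough to be coded again are kept with all their on-treatment time from index.

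Three things are at stake:

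- **Early incidence.** Angioedema is reported at Weeks 1, 4, 8, 26 and 52, and Section 7.1.1 says the ACEI risk is highest shortly after initiation. Dropping patients with short records removes early person-time.
- **The other safety events.** A patient who dies soon after, say, renal impairment and before a second HF code leaves the cohort together with the event.
- **The comparison.** Sacubitril/valsartan is indicated for HF, whereas Section 7.1.1 notes that HF patients often receive ACEIs for hypertension or other conditions. A lone HF code confirmed late is therefore plausibly more common among ACEI users, so the selection need not cancel between cohorts.

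**Working it through.** **Inputs.** GePaRD launch January 2016, data end December 2019, duration 48 months (Table 7-1). HF window: before index or up to 90 days after (Section 7.2.4). Feasibility initiators: 4,724 of 5,185 from GePaRD (Section 7.1.2). Cohort 3: more than 89,000 without and almost 567,000 with ARS and GePaRD. Cohort 4: more than 21,500 without and 116,041 with them (Sections 7.1.1 and 7.1.2). Planned initiators: about 29,000 (Abstract).

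**Step 1: the plan's own figure.** January 2016 to December 2019 inclusive is 4 × 12 = 48 months, as Table 7-1 states.

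**Step 2: longest delay to the confirming record.** 1 January 2016 to 31 December 2019 is 1,460 days, and 1,460 / 365.25 = 4.0 years. Of this, 1,460 − 90 = 1,370 days lie beyond the HF window. For index dates in mid-2016, mid-2017 and mid-2018 the longest delay is about 3.5, 2.5 and 1.5 years.

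**Step 3: apply the rule as written to two illustrative patients.**

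| | Patient A | Patient B |
|---|---|---|
| First outpatient HF claim | 2015 | 2015 |
| ACEI index | 2016 | 2016 |
| After index | stays insured, second HF claim 2019 | dies or leaves the insurer in 2017, no second claim |
| HF date under the rule | 2015 | none, unconfirmed |
| In cohort? | yes, follow-up from 2016 | no |

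The two are indistinguishable at index and at index + 90 days; only later information separates them. Replacing A's second outpatient claim with a 2019 primary discharge diagnosis gives the same result, because the dating rule covers both routes.

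**Step 4: how much of the study the rule governs.**

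- Feasibility initiators: 4,724 / 5,185 = 91.1%, leaving 461 from the other six databases.
- That cohort against plan: 5,185 / 29,000 = 17.9%, so the final GePaRD share may differ.
- ARS and GePaRD together, cohort 3: (567,000 − 89,000) / 567,000 = 84.3%.
- ARS and GePaRD together, cohort 4: (116,041 − 21,500) / 116,041 = 81.5%.

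The last two shares cannot be split by database, and ARS needs only one diagnosis.

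**Step 5: what cannot be computed.** The protocol gives no count of patients whose confirming record falls after index + 90 days, so no change in a rate or hazard ratio can be derived.

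**The case against.** **The note can be read more tightly.** It qualifies a criterion that already carries the 90-day window, so confirmation might be meant to fall inside it, and the analysis plan may say so. This has some force. But the note writes out the algorithm without deferring it, and its dating rule points the other way: the date to be tested is that of the earliest HF record.

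**The protocol reports a relevant check.** Section 7.1.2 says the third and fourth interim reports analysed sacubitril/valsartan users whether or not HF was recorded and found no differences in incidence rates. Section 3 says both reports included GePaRD. If dropping the HF requirement leaves the rates unchanged, the timing of its confirmation is unlikely to matter much there. This stands, with limits. For angioedema it rests on few events: the fourth-interim rate of 0.7 (0.4 to 1.1) per 1,000 patient-years fits roughly 13 to 23 events if the interval is an exact Poisson one. It does not cover ACEI users or hazard ratios, and it will not be repeated in the final analysis.

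**Many patients will be confirmed before index.** GePaRD holds diagnoses from 2004 (Section 7.4.7), so this is likely. It limits the size of the problem but does not remove it.

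**The angioedema limit is a poor model for HF.** Agreed. Three months suits an acute event; HF is chronic, and widely spaced codes do not make it less real. The contrast shows only that the protocol bounds a confirming record in time elsewhere.

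**Stronger readings that the documents do not support.** A reader might infer that 91% of initiators, or 84% of cohort 3, are affected. Those are shares of data supply, not of late confirmation, and the second includes ARS. A reader might also infer that time up to confirmation is guaranteed free of angioedema. It is not: the rule requires staying alive and insured, and a patient with angioedema who remains insured can still be coded again and counted. Nor is the whole interval counted person-time, because follow-up ends when treatment stops or changes.

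**Conclusion.** The point holds. Followed as written, the GePaRD rule lets records up to about 4 years after index decide who was in the cohort at index, conditioning entry on survival and continued insurance. It applies in the database that supplied most feasibility initiators, and it has no counterpart in the single-diagnosis databases beyond the shared 90-day allowance.

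The number affected is unknown and the net direction of any bias uncertain. For sacubitril/valsartan incidence rates the effect is probably small. The exposure is mainly in the ACEI cohorts (secondary objectives) and in the hazard ratios, which the protocol labels exploratory. The conclusion assumes the rule is programmed as printed and that no unseen document adds a cut-off. It is worth correcting because the correction is cheap and no planned analysis described in the protocol would reveal the problem.

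**What to change.** Amend the GePaRD note so that the complete confirmation, whether the primary discharge diagnosis or both outpatient diagnoses, must be recorded within the window already used for HF: before index or within 90 days after. Keep the date of the earliest HF record as a descriptive onset date only. In the attrition table, report for each of the four cohorts how many GePaRD patients are lost because confirmation came later.

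No maximum interval between the two outpatient claims is needed. Once the cut-off is set, an interval limit adds nothing against this selection and would discard genuine chronic HF.

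The cost is one sentence in the note and a filter on dates already held. The downside is somewhat fewer GePaRD patients, including some with newly diagnosed HF not yet confirmed by the cut-off. The 90-day look-ahead common to all databases remains.
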